Coordinating investigator	PD [name], Klinik für Neurochirurgie, Universitätsklinikum Münster, [name]
Investigators	[name]
Title	Multi-center-registry trial on surgical outcome and quality of life in juxta-medullary tumors
Indication	Adult patients operated on juxta-medullary tumors
Study objectives	
Primary objectives:
 
Primary objectives are to assess and define benchmarks of the surgical outcome in the form of extent of resection, functionality, and quality of life after resection of juxta medullary tumors
 
Secondary objectives:
 
Assessment of variables leading to better outcome through regression analysis:
 
1. Influence of surgical approach on functionality, pain, and quality of life2. Comparison between patient with severe neurological (McCormick scale 3-5) to patients with mild deficits (McCormick 1-2)3. Role of IOM in extent of resection and neurological deficits 
Assessment of treatment variations:
 
1. Assessment of risk factors for incomplete resection2. Non inferiority of unilateral approach to achieve gross total resection of spinal meningioma, schwannoma and cauda ependymoma3. Role of bed rest after surgery to prevent cerebro-spinal fluid leakage4. Influence of laminectomy on cerebro-spinal fluid leakage 
Quality indicators: assessments of length of hospital stay, 30- and 90-days readmissions, 30- and 90-days re-surgery, nosocomial infections

Inclusion/Exclusion criteria	
Inclusion criteria
 
• Adult, age ≥ 18 years, patients treated on intraspinal, extra medullary tumor• Patients must have sufficient cognitive and language skills to give informed consent

	
Exclusion criteria
 
 • Absence of informed consent • Lack of ability to consent • Primary bone tumors invading the intra-spinal space • Vertebral metastasis
	
Primary Outcome
 
 • Quality of life based on the questionnaire (EQ-D5) • Extent of tumor resection (see CRF): 
 according to surgeon: 
 1. Meningioma: Simpson grade 1 and 2 2. Schwannoma: complete resection, including nerve root 3. Cauda ependymoma: complete resection, including filum terminale according to postoperative MRI, 3 months after surgery 4. Other: surgeon's decision • Neurological status (McCormick Score) (see CRF), 3 months after surgery
Outcome(s)	
Secondary Outcome
 
Imaging: preoperative and postoperative MRI (3 months) according CRF
 
 • Volumetry • Spinal canal occupancy ratio in % 
Further patient reported outcomes:
 
 • Functionality: Neck disability index (NDI) for tumors in the cervical spine, Oswestry disability index (ODI) for tumors in the thoracic and lumbar spine (see CRF) • Local and radicular pain (VAS 1-10) (see CFR) • Neurological status: motor function of each limb, ataxia and gait (mJOA score) (see CRF) • HADS score- based score for anxiety • Questionnaire on bladder, bowl, sexual functionality

	
Quality indicators (QI):
 
Length of hospital stay
 
30- and 90-days readmission
 
Nosocomial infections
 
Blood loss
 
Duration of surgery
 
Progression of the disease or recurrence
 
Other adverse events
 
Mortality
 
Assessment of adverse events according to Common Terminology Criteria for Advers Events (CTCAE) 5.0 and severity according to the Ibañez scale (see CRF)
 
CSF leakage is defined as one, when CSF leakage is identified on imaging of clinically and treatment is required: operative or conservative (Lumbar drain for example)
 
Postoperative kyphosis or deformity is defined, when symptomatic (for example pain) or evident on imaging (for example kyphotic fracture on MRI)

Study design	Registry trial
Statistical analysis	
Primary Outcome
 
Improvement of neurological function, quality of life, and extent of resection
 
Secondary Outcome
 
Descriptive data analysis of clinical parameters is performed. Confidence intervals for relevant treatment effects are calculated using univariate and multi-variate statistical tests

Number of cases	100 patients
Time period	February 2025 until June 2027
Number of centers	N= X

1.2 Flow chart

	Admission	Surgery	Discharge	3 months follow up	12 months follow up*
Assessment of inclusion and exclusion criteria	X				
Informed consent/assent	X				
neurological status: motor function, ataxia, reflexes, cauda symptoms	X		X	X	X
VAS Back pain, radiculopathy	X		X	X	X
McCormic score	X		X	X	X
Imaging (MRI)	X			X	X
EQ-5D	X			X	X
mJOA/NDI/ODI and further scores	X			X	X
Approach		X			
LOS			X		
30 and 90 days readmission				X	
Adjuvant treatment				X	X
Adverse events	X	X	X	X	X

* Further follow and documentation is possible and recommended

2. Introduction

2.1 Background information

Juxta-medullary tumors are mostly benign tumors in the spinal canal that may cause neurological deficits due to spinal cord or nerve root compression. The knowledge about the natural course of the disease, optimal treatment regarding timing of surgery and surgical approach are based on case series from different institutions around the world (Montano et al., 2016; M. Safaee et al., 2015, 2016; M. M. Safaee et al., 2017; Safavi-Abbas et al., 2008; Schwake et al., 2018; Takahashi et al., 2022). Moreover, little is known about the long-term clinical and functional outcome after tumor resection, indicators of quality of treatment and quality of life after surgery.

Main treatment option of juxta-medullary tumors is a neurosurgical resection. The main goal of the surgery is to decompress the neuro structures in order to reveal neurological deficits. However, achieving gross total resection (GTR) is important in order to achieve long progression free survival (PFS) (Lenzi et al., 2017; Nanda et al., 2015; Ottenhausen et al., 2019; Ozawa et al., 2007). Therefore, the surgeon should choose the appropriate surgical approach to achieve these goals. Several publications show that GTR, whenever possible, is essential, as subtotal resection is the main reason of tumor regrowth or recurrence. Moreover, revision surgery due to tumor recurrence is one of the main risk factors of unfavorable outcome, probably to intradural adhesions, related to the first procedure. Due to the mostly benign nature of juxtamedullary tumors, it would be very difficult to evaluate overall survival (OS) and progression free survival (PFS) within this progressive registry in the short run. For this reason, data should be kept for late cohort analysis after longer intervals. Probably up to 20 years, as previous publications reported recurrence of spinal meningioma after GTR 10 years or more after surgery.

On the other hand, too large exposure may lead to impaired recovery after surgery, eventual higher blood loss during surgery and thus longer stay in hospital (LOS) and impaired quality of life. Moreover, extensive bone resection may lead to spinal instability requiring instrumentation, during index surgery or during further follow up in case of postoperative deformity (Abumi et al., 1990; Jiang et al., 2022; Lee & Teo, 2004; Mummaneni et al., 2020; Raysi Dehcordi et al., 2012).

In addition to the oncological outcome, the neurological outcome is also very important. Depending on the localization of the tumor, its form and compression of intra-spinal structures such as the spinal cord or nerve roots many patients develop neurological deficits. Besides GTR the other goal of resection is the neurological recovery of these patients. Previous reports show that the time point of surgery is important in order to achieve full recovery (Schwake et al., 2018). However, most of the data is derived from retrospective case series. One of the aims of this registry is to prove this hypothesis. These neurological deficits are, as mentioned above, related to the localization of the tumor within the spine, Tumors in the cervical spine would cause mainly gait ataxia, spasticity, and weakness in the upper extremities while tumors in the lumbar spine would lead to deficits in the lower extremities in combination to disturbances of bladder, bowel, and sexual functions. These functions should be evaluated and monitored, before and after treatment.

Other concerns are safety requirements in order to prevent peri-operative complications. For example, the role of intra-operative neurophysiological monitoring. Some authors recommend the utilization intra operative monitoring, however, the evidence level is very low (Jesse et al., 2022; Thakur et al., 2021). Other open questions are for example the utility of microscope, methods for dura closure and thrombosis prevention.

On the other hand, some tumors can be treated with irradiation, some studies showed efficacy of this method mainly in the case of Schwannomas and meningiomas. In case of residual tumor or tumor progression irradiation can be also performed to prevent further growth (Chang & Lee, 2013).

Lastly, in comparison to the methods mentioned above, a wait-and-see approach can be used for asymptomatic patients or those with mild symptoms. In this case, clinical and imaging examinations are performed at regular intervals to check the neurological status and the tumor. This can also be done for longer periods of time because of the benign nature of these tumors with the slow growth. in case of new neurological deficits or progression surgical treatment should be advocated. Overall, it is not certain at what point therapy is indicated, especially in asymptomatic patients. Because many of these tumors are discovered by coincidence during imaging, which was performed due to other symptoms.

2.2 Rationale of the study

The rationale of the trial is to define benchmarks on quality of life, functionality and neurological outcome after resection of juxtamedullary tumors. Furthermore, to assess and define benchmarks of quality indicators of the treatment. These measurements would be essential for future studies.

Further rationales are to find out the optimal timing, method, and approach to treat juxta-medullary tumors. Because of the low incidence of juxta-medullary tumors, a multi-center trial seems to be essential. This would allow us to analyze a large number of patients, much more than any other published paper. Moreover, the different protocols and standards approaches in each center would allow conducting Comparative Effectiveness Research (CER).

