2.3 Methodology

All patients treated in one of the study centers are recorded in a databank (Redcap, see below), which includes information about admission, symptoms, other diseases, treatment, quality indicators and questionnaires regarding quality of life and functionality. Data should be recorded in an anonymized in each center (see below).

For the analysis the CRF includes information about admission, surgery, discharge, and 3 months (90 days) after surgery. In addition, patients should fill out questionnaires on quality of life (EQ-D5) and functionality (ODI or NDI). Later, yearly visits can be completed to have long term results in the future regarding progression free survival (PFS) and overall survival (OS). The CRF is attached to this document.

Univariate and multivariate statistics would be applied to prove which variables might lead to a favorable or unfavorable outcome.

A minimum number of one hundred (N=100) inclusions seems to be adequate in order to perform reasonable analysis. In the event of nonsufficient recruitment, results and further recruitment would be discussed two years after initiation of the study, and annually thereafter.

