2.4 Risk-Benefit Analysis

2.4.1 Risk expected for participants

No risk whatsoever awaits the participants in the study. All examinations and interventions will be performed according to clinical routine. Refusal to participate in the study will not result in any disadvantages for the patients. Participants will be treated exactly like non-study participants, based on the therapy standards of the respective study center

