3.1 Study Site Selection

Due to the rare nature of juxta-medullary tumors and in order to have the opportunity to compare different treatment methods, the trial is planned as a multi-center trial.

So far, 5 centers have expressed interest in participating in the study.

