3.2.3 Distribution of Gender in the Study Population

All patients treated on juxta-medullary tumors can be invited to participate in the study; distribution of Gender varies depending on histology. For example, spinal meningiomas are up to 80% in female patients (Schwake et al., 2018).

4. Patient Registration

Patients who are cared for at one of the study sites and who are possibly eligible will be invited for study participation. Once written informed consent in participation has been given, the center can register the patient in the electronic data base (Redcap).

Should inclusion criteria fail, or exclusion criteria arise during the following screening process, the patient must be reported to the study coordinator immediately and the patient will be withdrawn from the study.

5. Assessment of Safety

Patients are treated according to the protocol of each center, the participation in the trial does not cause any disadvantage for these patients. Both patients' safety and possible adverse events are

subjects of this study.

6. Statistics

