6.2 Secondary outcome

Descriptive data analysis of clinical parameters will be performed. Confidence intervals for relevant treatment effects are calculated using univariate and multi-variate statistical tests.

Patients' data will be compared to historical cohorts and equivalence, or superiority of care will be described.

Further analysis will be performed as comparative effectiveness research (CER) as described above. When applicable cohorts will be matched in a case-control mode.

7. Documentation, Data Management, Archiving

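### Comparative effectiveness is to be drawn from differences in practice between about five centres, which cannot work for a practice that is wholly a centre's standard and needs a centre-based comparison for one that partly is

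*Protocol*

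**What the plan says.** Section 2.2 of the protocol presents variation in practice between centres as the basis for comparing treatments: "the different protocols and standards approaches in each center would allow conducting Comparative Effectiveness Research (CER". Section 3.1 gives the same reason for the design, next to rarity: "in order to have the opportunity to compare different treatment methods, the trial is planned as a multi-center trial". Treatment is not allocated by the study. Section 5 says "Patients are treated according to the protocol of each center", and section 2.4.1 describes care as "based on the therapy standards of the respective study center".

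The number of centres is not fixed. Section 3.1 says "So far, 5 centers have expressed interest in participating in the study", and the synopsis holds only a placeholder. On size, the Methodology section says "A minimum number of one hundred (N=100) inclusions seems to be adequate in order to perform reasonable analysis", without a calculation.

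The synopsis lists as secondary objectives the influence of surgical approach, the role of intraoperative monitoring (IOM), non-inferiority of the unilateral approach, bed rest and CSF leakage, and laminectomy and CSF leakage. For analysis, section 6.2 says "Confidence intervals for relevant treatment effects are calculated using univariate and multi-variate statistical tests", and later "When applicable cohorts will be matched in a case-control mode". Neither sentence mentions centre.

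**The concern.** Section 2.2 makes a claim about identification: that differing centre standards are enough to learn which treatment works better. That is a design statement, not a modelling detail that a statistical analysis plan could fill in later.

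If every patient at some centres receives a practice and no patient at the others does, comparing the practice means comparing two small groups of centres. Those groups also differ in surgeons, case mix and all other care. Two of the outcomes leave room for local judgement as well. A CSF leak counts only if it was treated, and extent of resection rests partly on the surgeon's own assessment.

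At stake is that differences between a handful of hospitals are published as effects of bed rest, monitoring or approach, with intervals that look more precise than they are.

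**Working it through.** **Plan's own figure.** The 100 patients cannot be reproduced. The protocol gives no significance level, power, effect size, rate, margin or intracluster correlation (ICC) for it.

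**Inputs.** From the protocol: 100 patients (a minimum) and 5 centres (interested, not fixed). Assumed: equal centres, so m = 100/5 = 20; ICC of 0.01, 0.05 or 0.10; and a practice used mainly in 3 centres and less in the other 2.

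**Step 1: identification.** If a practice is used by all patients in some centres and by none in the others, the treatment indicator is a sum of centre indicators. A model with a centre term then cannot estimate the treatment effect. A model without one estimates treatment plus centre difference. Matching across centres pairs a patient from a using centre with one from a non-using centre, so each pair still contains the centre difference. Matching within centre finds no pairs.

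**Step 2: size when the practice is fully centre-level.** Design effect DE = 1 + (m − 1) × ICC. Effective N = 100/DE. Real type I error of a nominal 5% test that ignores centre = 2 × [1 − Φ(1.96/√DE)].

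| ICC | DE | Effective N | Type I error, formula | Type I error, simulation |
|---|---|---|---|---|
| 0.01 | 1 + 19 × 0.01 = 1.19 | 84 | 7.2% | 6.8% |
| 0.05 | 1 + 19 × 0.05 = 1.95 | 51 | 16.0% | 16.6% |
| 0.10 | 1 + 19 × 0.10 = 2.90 | 34 | 25.0% | 25.5% |

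The simulation used 5 centres of 20, no true effect, 4,000 runs and a t-test. Its Monte Carlo standard error near 5% is √(0.05 × 0.95/4000) = 0.3 percentage points.

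**Step 3: size when the practice only partly follows the centre.** What matters is the share ρ of the variation in treatment that lies between centres. Approximately, DE = 1 + (m − 1) × ICC × ρ.

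- 90% against 10% use: mean use 0.6 × 0.9 + 0.4 × 0.1 = 0.58. Between-centre variance 0.6 × 0.32² + 0.4 × 0.48² = 0.1536. Total 0.58 × 0.42 = 0.2436. So ρ = 0.63.
- 70% against 30% use: mean use 0.54. Between-centre variance 0.6 × 0.16² + 0.4 × 0.24² = 0.0384. Total 0.54 × 0.46 = 0.2484. So ρ = 0.15.

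Type I error at ICC 0.01 / 0.05 / 0.10:

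| Use in the two groups of centres | Ignoring centre, formula | Ignoring centre, simulation | Centre fixed effect, simulation |
|---|---|---|---|
| 90% vs 10% | 6.4 / 12.1 / 18.6% | 7.0 / 12.8 / 19.8% | 5.7 / 5.0 / 4.9% |
| 70% vs 30% | 5.3 / 6.7 / 8.5% | 5.1 / 6.5 / 8.1% | 4.6 / 5.2 / 4.6% |
| 50% in all centres | 5 / 5 / 5% | 5.1 / 5.2 / 5.1% | 4.9 / 5.2 / 5.3% |

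A centre term therefore brings the error back to about 5% wherever the practice varies within centres. For a fully centre-level practice it gives no estimate at all.

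**Step 4: unequal centres.** With an assumed split of 40/25/15/10/10, the mean centre size weighted by patients is (1600 + 625 + 225 + 100 + 100)/100 = 26.5. DE becomes 1 + 25.5 × ICC = 1.26, 2.28 and 3.55, so equal sizes are the milder assumption.

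**Step 5: what a remedy can carry.** Section 2.4.5 puts CSF leak at about 1–4%, which is 1 to 4 events in 100 patients. A model with treatment, four centre terms and several clinical covariates cannot be fitted reliably to so few events.

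**The case against.** The best defence is that the protocol says little about the analysis, and what it leaves open may be handled well. A centre term, stratification or clustered variance commonly sits in the statistical analysis plan, which is not available here. Section 6.2 also foresees matching, which could be done within centre. This stands as far as interval width is concerned. A reader might infer from section 6.2 that the intervals treat all 100 patients as independent, but the protocol does not say so. The figures above show what would follow if centre were ignored, not what is planned.

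A reader might also infer that none of the listed comparisons can be separated from centre. The documents do not support that. Preoperative McCormick group is a patient characteristic. Section 2.1 describes the surgeon choosing the approach to suit the goals of surgery, which suggests choice by case, and the facetectomy question depends on tumour shape. IOM may also vary within centres. Even bed rest as a pure centre policy is a plausible reading rather than a stated fact.

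Nor do five centres make the error rates in step 2 optimistic. The few degrees of freedom widen a valid centre-level interval: with 3 degrees of freedom the multiplier is 3.18 instead of 1.96. They do not raise the error of a test that ignores centre, and the simulation agrees with the formula.

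Finally, the primary objectives are benchmarks, which this point leaves untouched, and the Aims section places the comparative hypotheses in the future. The second argument carries little weight, because the synopsis lists several of them as current secondary objectives.

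None of this answers step 1. For a practice fixed by centre, no analysis plan can recover the effect.

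**Conclusion.** The point holds in two parts. First, the claim in section 2.2 that practice variation makes comparative effectiveness research possible is not true for a practice that does not vary within centres. This needs no numerical assumption; it follows from treatment being set by centre, with only a handful of centres. Second, for practices that partly follow the centre, an analysis that ignores centre would be biased and its intervals too narrow, and the protocol does not say which kind of analysis is meant.

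The size of the second part runs from nothing (equal use) through a real error of 5–8% (70% vs 30% use) and 7–20% (90% vs 10%) to 7–25% (fully centre-level). These ranges assume 5 centres of 20 patients and an ICC between 0.01 and 0.10; neither the centre sizes nor the ICC is given in the protocol. The protocol should be changed, but the benchmark objectives and the patient-level comparisons are not at risk.

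**What to change.** In section 2.2, limit the claim: variation between centres supports comparisons only for practices that also vary within centres. In section 6.2, add two sentences. One states that treatment comparisons are stratified by centre, adjusted for centre or matched within centre wherever the practice varies within centres. The other states that practices without such variation are reported by centre, descriptively, with no effectiveness claim. A table of each practice by centre, drawn up before outcomes are compared, would show which comparisons fall into which group.

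For rare outcomes such as CSF leak, use centre stratification or a sparse or penalised model instead of the full covariate set.

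The cost is wording and modest extra analysis. The price in results is real: intervals become wider, and some questions, possibly bed rest among them, become descriptive.

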2.3 Aims

The goal of this study is to establish a multicenter cohort of patients operated on juxtamedullary tumors. With especial emphasis on functional outcome, quality indicators (QI) and quality of life after surgery three months after surgery. Causes of unfavorable outcome should be determined (Schipmann et al., 2017, 2019).

The main hypothesis is that early and less-invasive surgery with maximal extents of resection would lead to a more favorable outcome. In the future the registry would help assessing further hypothesis can be answered on the base of comparative effectiveness research (CER), examples of these hypothesis are:

1. Functional and neurological outcome in comparison to preoperative status. Comparison between Patients with good preoperative McCormick score (1-2) and those with a high preoperative score (3-5).
2. Risk-factors for non-favorable outcome
3. Non-Inferiority to achieve gross total resection via unilateral approaches
4. Question whether laminectomy as approach may cause more pain and impact quality of life
5. Risk factors for the development of CSF Leaks
6. Does bed rest prevent CSF leaks
7. Does laminectomy elevate the risk of CSF leaks
8. Does the utility of intraoperative neurophysiological monitoring (IOM) influence surgical outcome: rate of GTR and neurological outcome
9. Rate of postoperative kyphosis and deformity in laminectomy in comparison to non-laminectomy

10. Is facetectomy required for GTR of dumbbell tumors?

11. Risk factors for non-complete resection

Primary outcomes are determined by:

- Quality of life based on the questionnaire (EQ-D5)
- Extent of tumor resection (see CRF):
according to surgeon:
 1. Meningioma: Simpson grade 1 and 2
 2. Schwannoma: complete resection, including nerve root
 3. Cauda ependymoma: complete resection, including filum terminale
according to postoperative MRI, 3 months after surgery
 4. Other: surgeon's decision
- Neurological status (McCormick Score) (see CRF), 3 months after surgery

Secondary Outcome

Imaging: preoperative and postoperative MRI

- Volumetry
- Spinal canal occupancy ratio in %

Further patient reported outcomes:

- Functionality: Neck disability index (NDI) for tumors in the cervical spine, Oswestry disability index (ODI) for tumors in the thoracic and lumbar spine (see CRF)
- Local and radicular pain (VAS 1-10) (see CFR)
- Neurological status: motor function of each limb, ataxia and gait (mJOA score) (see CRF)
- HADS score- based score for anxiety
- Questionnaire on bladder, bowel, sexual functionality

Quality indicators (QI):

Length of hospital stay

30- and 90-days readmission

Nosocomial infections

Blood loss

Duration of surgery

Progression of the disease or recurrence

Other adverse events

Mortality

Assessment of adverse events according to Common Terminology Criteria for Adverses Events (CTCAE) 5.0 and severity according to the Ibañez scale (see CRF)

CSF leakage is defined as one, when CSF leakage is identified on imaging of clinicaly and treatment is required: operative or conservative (Lumbar drain for example)

Postoperative kyphosis or deformity is defined, when symptomatic (for example pain) or evident on imaging (for example kyphotic fracture on MRI)

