3.2 Study Population

3.2.1 Inclusion Criteria

- Adult, age ≥ 18 years, patients treated on intraspinal, extra medullary tumor
- Patients must have sufficient cognitive and language skills to give informed consent

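### The main hypothesis on early surgery and maximal resection claims more than a registry of operated patients can support, and for one primary outcome it is true by definition

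*Protocol*

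**What the plan says.** Section 2.3 Aims of the protocol names a single main hypothesis: "The main hypothesis is that early and less-invasive surgery with maximal extents of resection would lead to a more favorable outcome". It joins three exposures: timing, invasiveness and extent of resection.

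Timing is raised in two other places. In section 2.1, "Previous reports show that the time point of surgery is important in order to achieve full recovery" is followed, after a remark that most data are retrospective, by "One of the aims of this registry is to prove this hypothesis". Section 2.2 adds: "Further rationales are to find out the optimal timing, method, and approach to treat juxta-medullary tumors".

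The population is surgical. The synopsis gives the indication as "Adult patients operated on juxta-medullary tumors", and section 2.3 Aims says "The goal of this study is to establish a multicenter cohort of patients operated on juxtamedullary tumors". The inclusion criterion in section 3.2.1 is looser ("patients treated on intraspinal, extra medullary tumor"). However, the flow chart in section 1.2 runs from admission through surgery and discharge to follow-up, and has no path for unoperated patients.

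Section 2.1 also says that "a wait-and-see approach can be used for asymptomatic patients or those with mild symptoms", that surgery should be advocated on new deficits or progression, and that the right point for therapy is uncertain.

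Section 2.3 Aims lists three primary outcomes: EQ-5D, extent of resection, and McCormick score 3 months after surgery. The primary analysis in section 6.1 compares status before and after surgery.

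**The concern.** A claim about when to operate needs a population in which the timing decision is still open. By the protocol's own account, some patients wait and come to surgery when they worsen. Those who do not worsen are never recorded. Late-operated patients are therefore not a fair sample of patients for whom surgery was deferred, and follow-up is counted from surgery, so the waiting period itself is not observed. A difference between early and late surgery in this cohort mixes any effect of timing with the reason for operating.

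Extent of resection raises a separate problem. It is named as a cause of a favourable outcome and is also listed as one of the outcomes by which favourable would be judged.

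At stake is what the registry may conclude. If the text stands, a report could present a selected association as proof that early surgery is better, on a question the protocol itself calls uncertain.

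**Working it through.** The protocol gives no figure for timing that could be reproduced. It states no threshold for early, no expected difference and no outcome rates. The check is therefore a comparison of the text, followed by an illustration with assumed inputs.

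**Text**

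1. Claim: causal and about timing (2.3 Aims), to be proved (2.1), with optimal timing sought (2.2).
2. Population: operated patients (synopsis, 2.3 Aims, flow chart).
3. Entry of waiting patients: on new deficit or progression (2.1). Stable waiting patients do not enter.
4. Analysis: before-after (6.1), with no early-versus-late contrast. Timing is not named in the synopsis's secondary objectives or among the 11 example hypotheses in 2.3 Aims.

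The claim in step 1 is not matched by the population in steps 2 and 3, and the analyses in step 4 do not address it.

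**Illustration of the selection (all inputs assumed)**

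- Timing has no effect on outcome.
- A share *q* of patients would stay stable; the rest would progress.
- A favourable outcome occurs in 90% of stable and 60% of progressing patients, whenever they are operated.
- Early-operated and waiting patients have the same mix of the two types.
- Waiting patients are operated only if they progress.

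Early-operated patients: 0.90*q* + 0.60(1 − *q*) = 0.60 + 0.30*q*.

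Late-operated patients in the registry: 0.60, because only progressing patients are seen.

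Apparent benefit of early surgery: (0.60 + 0.30*q*) − 0.60 = 0.30*q*. The true difference between the two strategies is 0.

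| *q* | Early | Late, as seen | Apparent benefit |
|---|---|---|---|
| 30% | 69% | 60% | 9 points |
| 50% | 75% | 60% | 15 points |
| 70% | 81% | 60% | 21 points |

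A simulation with the same inputs gave 9.0, 15.0 and 21.3 points.

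**Reversal of the sign**

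Now drop the equal-mix assumption. Let a share *s* of the early group be patients with severe deficits who were never candidates for waiting, with favourable rate *g*. The early group then has (1 − *s*)(0.60 + 0.30*q*) + *s g*. This falls below 0.60 when *s* > 0.30*q* / (0.60 + 0.30*q* − *g*), which is possible for any *g* below 0.60. Early surgery would then look worse, again with no true effect of timing.

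**Extent of resection**

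Set the exposure (maximal resection) beside each primary outcome:

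- EQ-5D: a question that data can answer.
- McCormick score at 3 months: likewise.
- Extent of resection: exposure and outcome are the same quantity, so the statement is true by definition.

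**The case against.** The strongest defence is that the timing sentence in section 2.1 stands in a paragraph on patients with neurological deficits. It can be read as earlier versus later surgery among patients who are operated, for whom an operated cohort is the natural population. No objective, listed hypothesis or analysis compares surgery with observation, and the stated primary objective is to set benchmarks. The protocol also plans multivariate analysis (2.3 Methodology) and a comparison by preoperative McCormick grade, so baseline status is not ignored. The CRF may hold the dates needed, and the definition of early may properly sit in an SAP.

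Much of this stands, and it rules out several stronger readings that a reader might infer:

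- *That the timing hypothesis cannot be tested at all.* An adjusted association among operated patients can be estimated if onset or diagnosis dates are recorded.
- *That the bias must favour early surgery.* The 9 to 21 points rest on an equal prognostic mix. Section 2.1 reserves waiting for asymptomatic or mild patients, so severe cases may fill the early group.
- *That the hypothesis is circular throughout.* Extent of resection can legitimately predict EQ-5D or McCormick grade, and can be an outcome in another model.
- *That the registry loses its main purpose.* The benchmark objectives do not depend on this hypothesis.

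The defence does not remove the core of the point. Even among operated patients, those who waited enter because someone decided to operate, usually on worsening. Adjusting for preoperative McCormick grade does not settle this either: the grade may itself be a result of delay, so adjustment can remove the very effect under study. An SAP can define early, but it cannot add unoperated patients or change the protocol's main hypothesis.

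**Conclusion.** The point holds as a mismatch between claim and design. The main hypothesis, the aim to prove it and the search for optimal timing go beyond what an operated-only observational registry can show. The bias in an early-versus-late comparison is of unknown size and direction. The range in the table shows that it could be large enough to matter, but it is an illustration built on assumed rates and not a forecast for this registry. The by-definition problem is confined to one of the three primary outcomes. What rests on the protocol alone, without assumption, is the operated-only cohort, the route by which waiting patients reach surgery, and the double role of extent of resection. The point should be corrected before results are reported, and it leaves the benchmark objectives intact.

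**What to change.** In section 2.3 Aims, replace the main hypothesis with separate associations among operated patients:

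- **Timing:** time from symptom onset, or from diagnosis in asymptomatic patients, with 3-month McCormick grade and EQ-5D. Adjust for histology and level, and report with and without preoperative McCormick grade, because that grade may be a consequence of delay.
- **Approach:** surgical approach with the same two outcomes, adjusted for histology, level and preoperative McCormick grade.
- **Extent of resection:** one role per model. It is either an outcome of approach, and then not a covariate in the approach model, or a predictor of EQ-5D and McCormick grade in a model of its own.

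In sections 2.1 and 2.2, replace the wording on proof and on optimal timing with these associations. State that no conclusion on early surgery versus observation will be drawn.

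The cost is a change of wording, a weaker claim, and a symptom-onset or diagnosis date in the CRF if it is not already there.
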